## Protocol Summary

This document represents the protocol summary for the study on human subjects. The study will be carried out in accordance with ICH GCP, National Standard of the Russian Federation GOST 52379-2005 "Good Clinical Practice", World Medical Association Declaration of Helsinki, relevant requirements of the regulatory authorities as well as the study procedures.

## Title of Study

Multicenter double-blind placebo-controlled randomized parallel group clinical study of efficacy and safety of Prospekta in the treatment of cognitive, behavioral and psychiatric disorders in subjects with vascular dementia.

**Phase:** III

**Sponsor:** Company «MATERIA MEDICA HOLDING», Moscow, Russia

**Protocol No.** MMH-MAP-003

## Study purposes

- To evaluate efficacy of Prospekta in the treatment of cognitive, behavioral and psychiatric disorders in vascular dementia.
- To evaluate the safety of Prospekta in the treatment of cognitive, behavioral and psychiatric disorders in vascular dementia.

## Study objectives

- Evaluate and compare changes in cognitive functions in two groups (Prospekta and Placebo) after 24-weeks of treatment.
- Evaluate and compare changes in behavioral and psychiatric dementia symptoms in two groups (Prospekta and Placebo) after 24-weeks of treatment.
- Evaluate and compare the presence and nature of adverse events (AEs) in two groups (Prospekta and Placebo), including central nervous system AEs during therapy, their relationship with the study drug and other characteristics.

## Endpoints

### *Primary endpoint*

1. Change in mean MoCA score after 24-week therapy (vs. baseline).

### *Secondary endpoints*

1. Change in mean NPI-C score after 24-week therapy (vs. baseline).

### *Additional endpoints*

1. Change in mean MoCA score after 12-week therapy.
2. Change in mean NPI-C score after 12-week therapy.

3. Mean CGI-EI score after 24-week therapy.

## **Safety assessment**

- Changes in vital signs during the study.
- Occurrence and nature of adverse events (AEs) during the treatment, their intensity (severity), relation to the study drug, outcome.

## **Study design**

Design: double-blind placebo-controlled randomized parallel-group clinical trial. The study will enroll male and female patients aged 60-85 years inclusively diagnosed with vascular dementia verified at Visit 1 according to the criteria of The National Institute of Neurological Disorders and Stroke National Institute of Neurological Disorders and Stroke-Association Internationale pour la Recherche et l'Enseignement en Neurosciences - NINDS-AIREN. Severity of vascular dementia should be moderate or mild (10-24 points according to Mini-Mental State Examination - MMSE), without signs of depression (total Cornell Scale for Depression in Dementia (CSDD) score  $\leq 10$ ).

After signing patient information sheet (informed consent form) to participate in the study, at Visit 1 (from day -14 to day 1) complaints and medical history will be collected, objective examination, recording vital signs - blood pressure (BP), respiration rate (RR), heart rate (HR) will be performed and compliance of the patient's diagnosis with NINDS-AIREN vascular dementia criteria will be evaluated. The study investigator will assess cognitive disorders using MMSE and Montreal Cognitive Assessment (MoCA). The study investigator and the patient's caregiver will fill Neuropsychiatric Inventory Clinician (NPI-C), and CSDD scales. The patient will undergo brain MRI (in the absence of brain MRI data within the previous 12 months before inclusion in the study).

Concomitant therapy and concomitant diseases and conditions will be recorded.

If inclusion/exclusion criteria are met, the patient will be randomized to one of the two groups: group 1 will receive Prospekta 2 tablets twice daily; group 2 will receive Placebo using the study drug dosing regimen.

Treatment duration will be 24 weeks during which 6 Visits will be made. At visits 2 and 3 (week  $4 \pm 3$  days and week  $8 \pm 3$  days) the study investigator will make a phone call and collect the complaints, monitor the prescribed and concomitant therapy, evaluate therapeutic safety.

At visit 4 (week  $12 \pm 7$  days) the study investigator will collect complaints, record objective examination findings and vital signs, monitor the prescribed and concomitant therapy, evaluate therapeutic safety and compliance, dispense the study drug until the next visit. The study investigator and caregiver will fill NPI-C.

At visits 5 and 6 (week 16±3 days and week 20±3 days) the study investigator will make a phone call and collect the complaints, monitor the prescribed and concomitant therapy, evaluate therapeutic safety.

At visit 7 (week 24±7 days) the study investigator will collect complaints, perform objective examination, record vital signs, monitor the prescribed and concomitant therapy, evaluate therapeutic safety, evaluate compliance. The study investigator will fill MoCA and Clinical Global Impression Efficacy Index (CGI-EI). The study investigator and caregiver will fill NPI-C. During the study the treatment for concomitant diseases will be allowed with the exception of the drugs specified in the section "Prohibited concomitant therapy".

## **Inclusion and exclusion criteria**

### ***Inclusion criteria***

1. Subjects aged 60-85 years old inclusively.
2. Subjects with verified diagnosis of vascular dementia.
3. Presence of all the vascular dementia criteria according to NINDS-AIREN:
  - A. Presence of dementia, which is defined as a decline in cognitive function relative to the previous level of functioning, manifested by impairments in memory and two or more cognitive domains (orientation, attention, language, visuospatial functions, executive functions, motor control and praxis), preferably established during a clinical trial and confirmed by neuropsychological testing.  
The cognitive impairment must be so severe that it affects daily activity, reducing it independently of the physical consequences of the stroke.
  - B. The presence of cerebrovascular disease, confirmed by signs of focal damage on neurological examination, such as hemiparesis, lower facial weakness, Babinski sign, sensory deficit, hemianopsia or dysarthria associated with stroke (either a history of stroke or absence of such anamnestic information), and neuroimaging (CT or MRI) signs of cerebrovascular disease, including multiple infarcts in the territory of large vessels, or a single infarction in a strategically important area (angular gyrus, thalamus, basal ganglia, or the territory of the anterior or posterior cerebral arteries), as well as multiple lacunae in the region of the basal ganglia or white matter, or significant damage to the periventricular white matter, or a combination of the above lesions.
  - C. There is an association between dementia and cerebrovascular disease as follows:
    - a) onset of dementia within 3 months of stroke;
    - b) sharp deterioration of cognitive functions; or fluctuating, stepwise progression of cognitive impairment.

4. Availability of permanent caregiver throughout the study (nurse or relatives).
5. Total Mini-Mental State Examination (MMSE) score - 10-24.
6. Total MoCA score <26.
7. Total NPI-C aggression and agitation domain score  $\geq 14$ .
8. Absence of depression (total Cornell Scale for Depression in Dementia (CSDD) score  $\leq 10$ ).
9. Brain MRI confirming the diagnosis of vascular dementia within 1 year prior to enrollment (or brain MRI performed at enrollment visit).
10. Patients giving their consent to use reliable contraception throughout the study (for males).
11. Availability of signed patient information sheet and informed consent form for participation in the clinical trial.

***Exclusion criteria***

1. Signs of intracerebral hemorrhage, brain tumours causing dementia.
2. Alzheimer's disease, Parkinson disease, Lewy body dementia, multiple system atrophy, Jacob-Creutzfeld disease, Pick's disease, corticobasal degeneration.
3. Injuries of head (S00-S09) associated with impaired consciousness, cerebral contusion or open craniocerebral traumas.
4. Toxicity-related dementia (including drug-induced), multiorgan failure or metabolic and toxic disorders (chronic hypothyroidism, decompensated diabetes mellitus, avitaminoses, etc.).
5. Other psychiatric diseases besides dementia: mental disorders and behavioral disorders due to use of psychoactive substances (F10-19) schizophrenia, schizotypal and delusional disorders (F20-29).
6. Mental retardation (F70-79).
7. Inflammatory lesions of the brain with persistent neurological deficit.
8. Malignant neoplasms.
9. Previously diagnosed cardiovascular diseases with functional class IV (according to New York Heart Association, 1964).
10. Unstable angina pectoris, myocardial infarction or ischemic stroke within the last 6 months.
11. Female patients with childbearing potency.
12. Allergy/intolerance of any of the study drugs components including secondary to lactase deficiency.
13. Any conditions which, according to the investigator opinion, may interfere with the patient's participation in the study.
14. History of treatment noncompliance, mental diseases, alcoholism or drug abuse which will prevent from following the study procedures, according to investigator's opinion.

15. Participation in clinical trials for 3 months prior to enrollment in this study.
16. Use of any medications specified in "Prohibited concomitant medications" within 1 month before enrollment.
17. Patients who are related to any of the on-site research personnel directly involved in the conduct of the trial or are an immediate relative of the study investigator. 'Immediate relative' means husband, wife, parent, son, daughter, brother, or sister (regardless of whether they are natural or adopted).
18. Patients who work for OOO "NPF "Materia Medica Holding" (i.e. the company's employees, temporary contract workers, designated officials responsible for carrying out the research or any immediate relatives of the aforementioned).

### **Criteria for Withdrawal or Termination**

1. Screening failure.
2. Inability or refusal of the patient/caregiver to comply with the protocol requirements.
3. Necessity in medications prohibited within the study.
4. An adverse event requiring discontinuation of the study drug.
5. Eligibility error.
6. Patient's/caregiver's desire to complete the study early for any reason.
7. Participation in any other clinical trial.
8. Cases not specified by the protocol when, according to the investigator's opinion, further participation in the study harms the patient.
9. Unblinding.

### **Number of subjects**

It is planned to include 406 patients (203 per group), which is expected to yield at least 324 patients (162 in Prospeksa and Placebo groups) completing all protocol procedures.

### **Interim analysis**

Unblinded interim analysis is preplanned in the study: at the 30% of enrolled patient. Type I error at the analyses is governed by O'Brien-Fleming spending function, for type II error – the Pocock spending function is selected. Early study termination is planned due to both acceptance and rejection of null hypothesis. Interim analysis will be carried out on the data from the number of completing subjects established by the protocol. Number of subjects for interim analysis: 98 subjects (Prospeksa – 49, Placebo – 49). Number of subjects for final analysis: 324 subjects (Prospeksa – 162, Placebo – 162).

## Treatment

### Group 1

**Name of the medicinal product:** Prospekta

**Active ingredient:** Affinity purified antibodies to brain-specific protein S-100, modified – 10 000 MAU\*

\* MAU – modifying action units

**Excipients:** Lactose monohydrate (Ph.Eur., USP NF, BP) - 0.267 g

Microcrystalline cellulose (Ph. Eur., USP NF, BP) - 0.030 g

Magnesium stearate (Ph.Eur., USP NF, BP) - 0.003 g

**Method of administration:** Tablet for oral use. 2 tablets twice daily (approximately at the same time), outside the meal (between meals or 15 minutes before meals or fluids). Keep the tablets in mouth until completely dissolved.

**Dosage form:** Tablets.

**Description:** Flat cylinder-shaped scored beveled edge white to off-white tablets with a smooth, uniform surface.

**Storage conditions:** Store at a temperature not exceeding 25°C.

### Group 2

**Name of the medicinal product:** Placebo

**Active ingredient:** No

**Excipients:** Lactose monohydrate (Ph.Eur., USP NF, BP) - 0.267 g

Microcrystalline cellulose (Ph. Eur., USP NF, BP) - 0.030 g

Magnesium stearate (Ph.Eur., USP NF, BP) - 0.003 g

**Method of administration:** Tablet for oral use. 2 tablets twice daily (approximately at the same time), outside the meal (between meals or 15 minutes before meals or fluids). Keep the tablets in mouth until completely dissolved.

**Dosage form:** Tablets.

**Description:** Flat cylinder-shaped scored beveled edge white to off-white tablets with a smooth, uniform surface.

**Storage conditions:** Store at a temperature not exceeding 25°C.

### *Treatment duration*

Prospekta/Placebo treatment duration is 24 weeks.

### *Observation period*

In total the patients will be monitored for 24-26 weeks (screening up to 2 weeks, therapy - 24 weeks).

 USP – current US Pharmacopoeia.

 BP – current British Pharmacopoeia.

***Symptomatic (Standard) treatment***

[figure not shown]
During the study, the patient may receive therapy for concomitant diseases and conditions, with the exception of medications specified in the section “Prohibited Concomitant Treatments.”

***Prohibited concomitant therapy***

One month prior to the enrollment as well as during the study (from signing of informed consent form and screening) any therapy affecting cognitive and mental status of the subject the following products will not be allowed (ATC group is indicated in brackets):

1. Anchicnolongeric agents (N04A).
2. Psycholeptics (N05) including:
  - antipsychotics (N05A)
  - anxiolytics (N05B)
  - hypnotic and sedative drugs (N05C)
  - other hypnotics and sedatives (N05CM) including those of herbal origin.
3. Psychoanaleptics (N06) including:
  - antidepressants (N06A)
  - psychostimulants and nootropics (N06B) including other psychostimulants and nootropics (N06BX)
  - anti-dementia drugs (N06D).
4. Other nervous system drugs (N07) including:
  - parasympathomimetics (N07A)
  - antivertigo preparations (N07C)
  - other nervous system drugs (N07X).
5. Heme products (B06AB): Actovegin.
6. Purine derivatives (C04AD): Pentoxifylline.
7. Dihydropyridine derivatives (C08CA): Nimodipine.
8. Substances of other pharmacological group with a nootropic ingredient including:
  - general tonic agents and adaptogens – herbal; melatonin, lecithin, acetylaminosuccinic acid etc.
  - antihypoxants and antioxidants – ethylmethylhydroxypyridine succinate, citicoline, all vitamins, etc.
  - metabolic agents.
9. Drugs that previously caused allergic reactions in patient.
10. Products containing ultrahigh dilutions (Tenoten, Proprotein-100, Divaza, etc.).
11. Homeopathic products with nootropic or psychoactive effect.
12. Any unauthorized product and/or vaccine.

## Study design scheme

## Schedule of study procedures

Procedure/visit	Visit 1 From day - 14 to day 1	Visit 2 Week 4±3 days (phone)	Visit 3 Week 8±3 days (phone)	Visit 4 Week 12±7 days	Visit 5 Week 16±3 days (phone)	Visit 6 Week 20±3 days (phone)	Visit 7 Week 24±7 days
Informed consent	+						
Patient registration in IVRS and assignment of a personal code		+					
Demographics	+						
Collection of complaints	+	+	+	+	+	+	+
Medical history	+						
Concomitant conditions and diseases	+	+	+	+	+	+	+
Physical examination	+			+			+
Vital signs (HR, RR, BP)	+			+			+
Matching vascular dementia diagnosis with NINDS-AIREN criteria		+					

Head MRI or analysis of findings of MRI made within 1 year prior to enrollment	+						
Concomitant therapy	+	+	+	+	+	+	+
Filling MoCA	+			+			+
Filling MMSE	+						
Filling NPI-C	+			+			+
Filling CSDD	+						
Inclusion/exclusion criteria	+						
Randomization	+						
Dispensing of study drug	+			+			
Study drug accountability and return				+			+
Treatment compliance				+			+
Evaluation of study treatment safety	+	+	+	+	+	+	+
Filling CGI-EI scale							+
Visit completion	+	+	+	+	+	+	+
Study completion							+ 

### ***Evaluation of sample size***

The sample size was assessed in accordance with the following rules and assumptions:

1. Statistical assumptions:
  - 1.1 the power of statistical tests ' $P = (1 - \beta)$ ' is 80% (the probability of correct rejection of the null hypothesis is 0.8)
  - 1.2 the probability of a type I error is less than 5% (the probability of false acceptance of the alternative hypothesis is less than 0.05)
  - 1.3 type 1 error is distributed between the primary and secondary criteria in 1:1 ratio
  - 1.4 statistical criteria of comparisons will be two-sided, unless specified otherwise

---

 Holder of license: OOO "NPF "Materia Medica Holding", No. 70100045.

- 1.5 calculation of the sample size will be based on the assumptions concerning the effect declared in the primary efficacy criterion of the protocol
- 1.6 ratio between Prospekta and Placebo sample sizes is 1:1 (1 Prospekta patient per 1 Placebo patient)
- 1.7 statistical hypotheses - null and alternative hypotheses on the difference between study drug and placebo under the dosing regimen used:  
Primary endpoint:

$$H_0: \mu_1 - \mu_2 = 0$$

$$H_a: \mu_1 - \mu_2 \neq 0$$

where  $\mu_1$  - change in total MoCA score in Prospekta group,  $\mu_2$  - change in total MoCA score in Placebo group

Secondary endpoint:

$$H_0: \mu_1 - \mu_2 = 0$$

$$H_a: \mu_1 - \mu_2 \neq 0$$

where  $\mu_1$  - change in total NPI-C score in Prospekta group,  $\mu_2$  - change in total NPI-C score in Placebo group

- 1.8 calculation of sample size for statistical criteria was made using the following program code:

Proc seqdesign errspend;

Design nstages = 2

Info = cum (0.3,1)

Method (alpha) = UNI (rho = 0.5 tau = 0)

Method (beta) = UNI (rho = 0 tau = 0)

Stop = both

Alpha = 0.025

Beta = 0.2

Samplesize model = twosamplemean (meandiff = 1.3 stddev = 3.53)

Run

- 1.9 Full sample size will be determined using the formula:

$$N_T = N_{PP} / (1 - K_B)$$

where  $N_T$  – full sample size;  $N_{PP}$  – result of calculation in c. 1.8, i.e. scheduled number of patients completing the study per protocol;  $K_B$  – withdrawal rate.

## 2. Assumptions on expected treatment effects.

It is assumed that the difference between the changes in the mean total MoCA score in the Prospekta and Placebo after 24 weeks of treatment will be 1.3 points with a standard deviation of at least 3.53.

Therefore, group size needed to compare Prospekta and Placebo will be **162** subjects for each group. Given potential withdrawal of at least 20% patients (**KB = 0.2**) during the study for various reasons, at least **406** subjects will be required to sign informed consent, with **203** patients per group (see cl. 1.9).

Minimum detectable effect for secondary criterion (change in total NPI-C score) at fixed sample size is supposed to be equal to: 7.36 (this being lower than clinically relevant change) at standard deviation of total score of 20 [13].

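### The 7.36-point NPI-C detectable effect is the MoCA two-stage effect rescaled; it has 80% power only if NPI-C stops on its own boundaries, and the plan's single study-level stop does not provide for that

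*Combined protocol and SAP*

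**What the plan says.** All references are to the combined protocol and SAP.

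- *Evaluation of sample size*, clause 1.3: "type 1 error is distributed between the primary and secondary criteria in 1:1 ratio". With 0.05 overall, MoCA and NPI-C get 0.025 each. Clause 1.4 adds that "statistical criteria of comparisons will be two-sided, unless specified otherwise". Clause 1.7 gives each endpoint its own null hypothesis, and nothing makes the NPI-C test conditional on MoCA.
- Clause 1.5: "calculation of the sample size will be based on the assumptions concerning the effect declared in the primary efficacy criterion of the protocol". The code in clause 1.8 accordingly has "Samplesize model = twosamplemean (meandiff = 1.3 stddev = 3.53", with two stages at 30% and 100% information, alpha 0.025, beta 0.2 and stopping in both directions.
- *Interim analysis*: "Early study termination is planned due to both acceptance and rejection of null hypothesis". The look is at 98 completers (49 per group) and the final analysis at 324 (162 per group). The endpoint whose null hypothesis counts is not named.
- *Assumptions on expected treatment effects*: the NPI-C detectable effect "at fixed sample size is supposed to be equal to: 7.36", with SD 20. The text adds that this is smaller than a clinically relevant change. It attaches no condition about the trial continuing past the interim.

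**The concern.** The 7.36 is the plan's only evidence that NPI-C is adequately powered. It comes from a two-stage design, so it implicitly gives NPI-C its own interim and final boundaries. The trial as described has one study-level stop, and its sample size and code were set on MoCA. If MoCA falls in the acceptance region at 98 completers, the study ends and NPI-C is left with 49 per group, whatever NPI-C itself shows.

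Half of the type I error is reserved for NPI-C, which makes the MoCA sample larger. Behavioural symptoms are one of the stated study objectives. A reader relying on the stated sensitivity would not know that it depends on how MoCA behaves at the interim.

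**Working it through.** **Inputs from the documents.** MoCA difference 1.3, SD 3.53; NPI-C SD 20; 49 and 162 completers per group; information 0.3 and 1; two-sided alpha 0.025; power 80%. **Assumed, not in the documents:** MoCA/NPI-C correlation 0, 0.3 or 0.5; MoCA drives the stop; the form of the NPI-C test after a stop.

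**1. Reproduce the plan's design.** An O'Brien-Fleming-type rejection boundary and a Pocock-type acceptance boundary, with 0.0125 per side, 80% power and a binding acceptance region, give:
- final critical value 2.158, and interim rejection at 2.158/√0.3 = 3.94;
- interim acceptance at |Z| < 0.662.

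The acceptance boundary is the drift × √information minus a constant. The drift is therefore (2.1577 − 0.6622)/(1 − √0.3) = 1.4955/0.4523 = 3.307. Then n = 2 × (3.307/0.3683)² ≈ 161.2 per group, where 0.3683 = 1.3/3.53. The plan states 162. The interim size is 0.3 × 161.2 = 48.4, and the plan states 49. The design is reproduced.

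**2. Reproduce 7.36.** At 162 per group and SD 20 the standard error of the difference is 20 × √(2/162) = 2.222. The two-stage detectable effect is 3.307 × 2.222 = 7.35. Direct rescaling gives 20 × 1.3/3.53 = 7.365. The stated figure is the two-stage one.

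**3. Single test at 162 per group.** (2.2414 + 0.8416) × 2.222 = 6.85. At a true 7.36, power is Φ(7.36/2.222 − 2.2414) = Φ(1.07) ≈ 86%.

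**4. Chance that MoCA stops the trial at the interim.** The acceptance region is an observed difference below 0.662 × 3.53 × √(2/49) = 0.47 points. The interim Z has mean (difference/3.53) × √24.5:
- MoCA effect 0: mean 0, acceptance stop 49%;
- 0.65: mean 0.91, acceptance stop 34%;
- 1.3: mean 1.82, acceptance stop 12%, plus a rejection stop of about 2%.

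**5. NPI-C power at 7.36 with a MoCA-driven stop.** At 49 per group, NPI-C power is Φ(0.368 × √24.5 − 2.2414) = 34% for a two-sided 0.025 test, and 2% at the 3.94 boundary. For zero correlation and no MoCA effect:
- single 0.025 test whenever the trial ends: 0.493 × 0.337 + 0.507 × 0.858 = 0.60;
- NPI-C on its own two-stage boundaries: 0.493 × 0.017 + 0.507 × 0.803 = 0.42.

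Simulation (2,000,000 trials per scenario) over correlations 0 to 0.5 gives:

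| True MoCA effect | NPI-C's own two-stage boundaries | Single 0.025 test when the trial ends |
|---|---|---|
| 1.3 (planned) | 70–72% | 78–79% |
| 0.65 | 53–56% | 64–68% |
| 0 | 40–42% | 59–60% |

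With no MoCA interference, NPI-C's own two-stage test has 80% power.

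**6. Type I error for NPI-C.** The value 2.158 holds 0.025 only with a binding NPI-C acceptance boundary. Without one, an interim test at 2.241 followed by a final test at 2.158 gives 0.028 to 0.030 at zero correlation. A single test at 2.241 when the trial ends gives 0.025 at zero correlation. The same simulation with the NPI-C difference set to zero shows some dependence on correlation: about 0.020 (no MoCA effect) to 0.028 (MoCA effect 1.3) at correlation 0.5.

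**The case against.** Four points can fairly be made for the plan.

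- **7.36 is not a miscalculation.** A reader might infer an arithmetic slip from the gap to 6.85. The documents do not support that: 7.36 reproduces, and the phrase about fixed sample size most likely means N held at 162 as set by MoCA. It is conservative for a trial that runs to the end. What remains is that the condition under which it holds is not stated.
- **The MoCA trigger is an inference.** A reader might conclude that the plan says MoCA alone stops the trial. It does not. The coded boundaries are standardised and would fit NPI-C at its own 0.025. If stopping for acceptance required both endpoints to be in the acceptance region, NPI-C power at 7.36 would be about 82–85% and the loss would disappear. No section states that rule, and clauses 1.5 and 1.8 point to MoCA.
- **The large loss needs a scenario the plan does not assume.** The 40–60% range combines no MoCA effect with a full 7.36 on NPI-C. It is tempting to say the alpha split exists for exactly that case, but clause 1.3 gives no such rationale. At the planned MoCA effect the loss is modest.
- **Ending a trial when the primary endpoint looks futile, at some cost to a secondary, is a legitimate choice.** This stands. The criticism is of the stated sensitivity, not of having an acceptance stop.

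**Conclusion.** The point holds as a correction to a stated sensitivity claim. The 7.36 has 80% power only under independent two-stage stopping for NPI-C. If the trial reaches 162 per group, 80% power is available at 6.85. If MoCA drives the stop, overall power at 7.36 falls below 80%: slightly to moderately if MoCA performs as planned, and substantially if MoCA shows little effect, as tabulated above.

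These ranges rest on an assumed correlation of 0 to 0.5, on 49 and 162 completers per group, on SD 20, on a symmetric binding MoCA acceptance region, and on the two NPI-C testing conventions shown. The least certain element is the MoCA-only trigger, which the plan leaves open. It should not be reported that NPI-C is powered at 40–60% as planned; that is the result for one unfavourable scenario.

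**What to change.** In *Assumptions on expected treatment effects*, give 6.85 as the NPI-C difference detectable with 80% power if the trial runs to 162 per group (SD 20, single two-sided 0.025 test). Add that 7.36 is not detectable with 80% power overall when the interim stop is driven by MoCA. Give the three power ranges there, with the correlation and the post-stop NPI-C test listed as assumptions.

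In *Interim analysis*, state that the MoCA null hypothesis triggers the stop, and how NPI-C is tested if the study ends there. Specify an NPI-C critical value that holds 0.025. For a single test at trial end the starting point is 2.241, checked over plausible correlations. The value 2.158 should not be used without a binding NPI-C acceptance boundary.

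The cost is a few sentences and a sensitivity claim that becomes conditional and less favourable. Sample size and study procedures do not change. Requiring both endpoints to be in the acceptance region before stopping is a separate design choice for the sponsor. It would mean fewer early stops (about 24% instead of 49% when neither endpoint has an effect and they are uncorrelated: 0.49 × 0.49), and it is not needed for this correction.
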